**June 2021**

**Research proposal**

**Title: Enhanced recovery after surgery program in a low and middle-income country: *Feasibility, safety, patient's acceptance, reduction of the length of hospital stay, bed turnover and cost benefits for laparoscopic cholecystectomy at CHUK***

This research proposal concerns a research project on minimally invasive surgery as new surgical techniques in Rwanda, which will include different studies to conclude into a PhD project in clinical research and public health at the college of medicine and Health Sciences.

This project is part of a laparoscopic surgery program in the Rwandan referral and teaching hospitals to improve the recovery of the patients after surgery especially after laparoscopic cholecystectomy, which will lead to a reduction of hospital of stay and a good bed turnover in surgical department.

## 1. Background

Enhanced Recovery After Surgery (ERAS) was started by a group of surgeons from Northern Europe who formed a research group with the aim to explore the ultimate care pathway for patients undergoing colonic resections. In the 1990s Henrik Kehlet had initiated this work with his innovative work on fast track surgery (1) (2), showing that most patients had recovered enough to be discharged 2 days after open sigmoid resections (3), when the length of stay for these operations was 10 days or more in most countries. The ERAS implementation program is a structured systematic implementation program successfully employed internationally in >25 countries. The ambition of the ERAS Society is to disseminate evidence- based principles for perioperative care and to support the development of new knowledge in perioperative medicine and surgical pathophysiology (4).

No single technique or therapy can eliminate postoperative morbidity and mortality. Therefore, it is necessary to resort to multimodal management where several treatments and clinical approaches are combined to reduce in a clinically relevant way the undesirable consequences of surgical aggression, improve patient rehabilitation and reduce postoperative morbidity and overall costs (1)(5)(6)(2).

An enhanced recovery program (ERP) after surgery consists of multimodal and multidisciplinary management to mitigate the surgical stress and the inflammatory response, and their consequences. Postoperative recovery is thereby improved and accelerated. The preoperative period is used to optimize the patient's medical condition (2). Patient education, perioperative instructions and setting achievable expectation, incorporating the patient as a vital component in his/her own wellbeing, and recovery are of utmost importance. Patients need to understand that unless they contribute to the care path presented to them by the ERAS team, optimal surgical outcome and recovery will not be achievable. The patient needs to understand that they have "skin in the game"(7) (8) (9) (10) (11).

Laparoscopic surgery has helped to minimize surgical trauma in an increasing number of surgical procedures and avoids drains. The anesthetist makes preferential use of loco-regional techniques, avoids perioperative fluid overload, and prevents postoperative nausea and vomiting. After surgery, early feeding and mobilization are encouraged and facilitated by a multimodal analgesia strategy that spares opioids and limits their side effects.

ERPs reduce the incidence of medical complications by 50 %, including fewer infectious complications and a possible positive impact on survival after oncologic surgery. Hospital length of stay is shortened (2)[SEP] (12) (13) (14) (7) (10).

ERAS has been shown to have important clinical and economic benefits and significant reductions in length of hospital stay and the implementation of ERAS pathways improves clinical outcomes and induces substantial economic gains. ERAS is the current surgical revolution (15) (16).

Cholecystectomy is one of the commonest general surgical operations. Laparoscopic cholecystectomy is currently the most favored approach. As it is associated with less postoperative pain and ileus, it allows early discharge of patients from the hospital (17) (18). Studies from the West have reported that 'day case laparoscopic cholecystectomy' is feasible and safe with success rate of between 69-92 percent (18) (19).

In two randomized groups comparing ambulatory care and overnight stay, the average hospital stay was 3.1 for overnight stay versus 1.7 for ambulatory care (Dirksen) and the ambulatory treatment was less expensive (20) (17). However, careful patient selection is essential in ensuring a high success rate (18).

ERAS is not known in Rwanda and there is no report from any sub African country describing laparoscopic cholecystectomy in ERP. We will conduct a prospective study to assess the feasibility; safety, patients' acceptance, LOS and bed turnover of laparoscopic cholecystectomy in a tertiary care hospital in the ERP.

## **2. Problem statement**

All surgeries, including laparoscopic surgery, represent a major stressor to the patient with possible sequelae for post-operative well being, including decline in functional capacity, cognitive ability, and even cancer spread. Comorbidities such as diabetes, ischemic heart and vascular disease, stroke, and others have a larger impact on postoperative morbidity and mortality than age (21) (10).

ERAS pathways have been successfully implemented in many surgical specialties, including gastrointestinal, hepato-biliary, pancreatic, urologic, gynecologic, and urologic surgery (22) (23) (24).

The strongest evidence so far has been described in patients undergoing open colorectal procedures (6) (25) (26). Combining minimally invasive laparoscopic surgery and ERAS has been shown to have important clinical and economic benefits and significant reductions in length of hospital stay, but its spread remains slow worldwide.

Implementation of ERAS pathways improves clinical outcomes and induces substantial economic gains (15) (16) (2), and is becoming the optimal strategy for many surgeries when technically feasible (27) (28) (10).

Laparoscopic cholecystectomy can be performed as a day-case procedure with a low rate of complications and admissions/readmissions. Patient acceptance in terms of quality of life variables is similar to that for cholecystectomy with an overnight stay. The day care strategy is associated with a reduction in cost (29).

Laparoscopic cholecystectomy in ERAS program should optimize the surgical outcome and improve a quick recovery and decrease the length of hospital stay. At the University Teaching of Kigali, the current practice is to admit patients for laparoscopic cholecystectomy 24 hours prior to surgery and to discharge most patients within two to three days of surgery with a rate of complications around 5%.

Patients overcrowd CHUK and the hospital bed management is a serious challenge. Patients coming far from their homes and with limited financial resources are suffering to get admitted in hospital for elective and none urgent surgeries like cholecystectomy, We believe that ERP can benefit the hospital with a rapid bed turnover rate, and reduces cost for surgery and hospitalization while providing to the patients with quality care and the same time increasing the comfort of the patient in the post-operative period and minimizing the postoperative complications.

The aim of our study is to assess the feasibility and safety of laparoscopic cholecystectomy in the ERP by decreasing the length of stay from 72 hours to 36 hours, hospital bed turnover and evaluate the adverse events and cost related in a tertiary care hospital in Rwanda

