### **3. Research Questions**

- Is ERAS protocol implementable in Rwanda Tertiary Hospital?
- Is laparoscopic cholecystectomy feasible, safe and cost-effectiveness in the context of ERP in our settings?
- Is possible to discharge laparoscopic cholecystectomy patients within 36 hours postoperative?

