## **4. Objectives of the study**

### **4.1. General Objective**

The general objective of this study is to test the implementation of ERAS protocol in laparoscopic cholecystectomy with the aim of decreasing of the length of hospital stay to 36 hours and assess its safety and patients' acceptance.

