### **4.2. Specific Objectives**

1. To assess the level of knowledge and practice of Health care professional about Enhanced recovery after surgery program.
2. To determine the frequency of postoperative adverse events and complications after laparoscopic cholecystectomy (tress, fatigue, nausea and vomiting)
3. To determine the average length of hospital stay and bed turn over after laparoscopic cholecystectomy
4. To determine the rate and reason of overnight and re-admissions
5. To assess the patients' acceptance of ERAS program and the overall satisfaction
6. To determine the patient cost benefit when ERAS is implemented correctly.

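### Reduced stay, better bed turnover and cost benefit or cost-effectiveness are aimed at, but no usual-care or pre-ERAS patient comparator is specified and the 72 h reference is unmeasured

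*Protocol*

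**What the plan says.** **Comparative wording.** The title promises "reduction of the length of hospital stay, bed turnover and cost benefits for laparoscopic cholecystectomy at CHUK". The aim in section 2 is "decreasing the length of stay from 72 hours to 36 hours", and section 4.1 repeats it "with the aim of decreasing of the length of hospital stay to 36 hours". Section 3 asks whether the operation is "feasible, safe and cost-effectiveness in the context of ERP in our settings". The sixth specific objective in section 4.2 is "To determine the patient cost benefit when ERAS is implemented correctly". Section 7 links the results to higher turnover and lower hospital costs for patients.

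**Descriptive wording.** The third research question asks whether it is possible to "discharge laparoscopic cholecystectomy patients within 36 hours postoperative". The third specific objective is "To determine the average length of hospital stay and bed turn over after laparoscopic cholecystectomy". Neither needs a comparator.

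**Current practice.** Section 2 says that the hospital's practice is to "admit patients for laparoscopic cholecystectomy 24 hours prior to surgery and to discharge most patients within two to three days of surgery". No data source, period or spread is given.

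**Design.** Section 5.1 calls the study prospective and cross-sectional and names no control, historical or before-after group. Section 5.3 introduces the ERAS protocol from November 2021 and enrols consecutive patients until at least 50 are reached. The only baseline it mentions is a survey of health professionals' awareness and knowledge.

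**The concern.** A reduction, a gain or a saving is a difference between two conditions, and the plan specifies patient data for one. Cost-effectiveness asks for more still: a difference in cost and a difference in effect between two strategies.

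As written, the only reference available for stay is the 72 h in the aim. A mean from the ERAS series would be set against a figure that the study does not measure, and the difference would be read as the effect of ERAS. No reference figure at all is given for turnover or cost.

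This is not a detail that a statistical analysis plan can settle. Such a plan can choose how to compare two groups, but it cannot supply a second group for which the design makes no provision.

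**Working it through.** **1. Is a comparator specified anywhere?** These are the places where one could appear.

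- Section 5.1, design: no comparison group is named.
- Section 5.1, sample size: based on a 5% proportion, 5-point precision and a population of 1600. n0 = 1.96² × 0.05 × 0.95 / 0.05² = 73.0. With finite-population correction, 73.0 / (1 + 72.0/1600) = 69.8, i.e. 70, so the upper end of the stated 50 to 70 is reproduced. The 5% is the operation's share of the surgical caseload, so the calculation concerns no comparison of stay, turnover or cost.
- Section 5.3, enrolment: one series, all under ERAS.
- Section 5.3, tests: ANOVA, chi-square and t tests are listed without naming groups.
- Section 5.3, regression for stay: patient and perioperative factors only, with no term for care period or for ERAS against usual care.
- Section 6, planned tables: average stay, cost, and a table relating stay to the independent variables. None sets ERAS against usual care.
- Section 9, timeline: data collection from July 2021, before ERAS starts in November, but the earlier months are not described as a patient comparison.
- Section 11, funds: medical file records appear within a budget line, with no historical series described.

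None of these specifies a usual-care or pre-ERAS patient group.

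**2. What reference do the Protocol's own figures imply?** Section 2 gives admission 24 h before surgery and discharge of most patients two to three days after it.

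- Post-operative stay: 2 × 24 = 48 h to 3 × 24 = 72 h.
- Total stay: 24 + 48 = 72 h to 24 + 72 = 96 h.

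So 72 h is the top of the first range and the bottom of the second.

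**3. What gain to 36 h follows?** The aim's own figures give 72 − 36 = 36 h (50%).

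| Clock used for both figures | Usual care | Gain to 36 h |
|---|---|---|
| Post-operative | 48-72 h | 48 − 36 = 12 h (25%) to 72 − 36 = 36 h (50%) |
| Total stay | 72-96 h | 72 − 36 = 36 h (50%) to 96 − 36 = 60 h (62.5%) |

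The stated 36 h gain is thus the largest value on one clock and the smallest on the other.

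**4. Which clock?** Research question 3 counts 36 h from surgery, and section 5.2.5 times discharge from surgery. The aim and the general objective refer to length of stay without a starting point. A post-operative reading is the more coherent, but the text does not fix it. It also does not say whether the 24 h pre-operative admission continues under ERAS.

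**5. What this does to a result.** Suppose ERAS patients averaged 48 h after surgery. Against 72 h this reads as 72 − 48 = 24 h saved; against 48 h it reads as 48 − 48 = 0. The second is the extreme lower end of the narrative range, so it is a worst case.

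**6. What the single series can give.** The proportion discharged within 36 h of surgery needs no reference. For illustration, 40 of 50 is 80%, with exact 95% confidence interval 66.3-90.0%.

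**The case against.** The strongest reply is that this is a feasibility study whose operative text is already largely descriptive. The third objective and the planned tables report average stay and cost, the third research question needs no comparator, and several of the quoted passages state aims rather than results. That stands, and it limits the point to the reduction, turnover and cost conclusions. It does not remove it: cost-effectiveness is a research question and cost benefit an objective.

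Several stronger readings are tempting, and the Protocol does not support them.

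- *The 72 h is baseless.* The account of current practice is local and compatible with it. The figure is unmeasured, not contradicted.
- *Pre-ERAS data will not be collected.* The July start, the file-records budget line and the list of tests leave that open. The July start may serve the staff survey. What can be said is that no comparator is specified.
- *The ERAS series is confined to Kigali by eligibility.* Section 5.3 says that patients in and near Kigali will be encouraged to take part; residence is not among the stated exclusions.
- *The turnover gain would be lost in the unit's 40 beds.* No unit-wide rate is proposed. The objective concerns turnover after this operation.
- *A file review would certainly detect a 12 h difference.* The Protocol gives no SD for stay. With an assumed SD of 24 h and two-sided 5% significance, power for a true 12 h difference is about 78% with 75 against 50 patients, and about 65% with 40 against 50.

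**Conclusion.** The point holds for the comparative conclusions only, and should be corrected. With one specified ERAS series, the study cannot show that stay, turnover or cost changed, or that ERAS is cost-effective. The implied reduction in stay is 12-36 h if both figures are post-operative and 36-60 h if both are total stay, and nothing specified would establish where in those ranges usual care lies.

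These ranges take the account of current practice literally. It covers most patients, so some stays may be longer, and the ranges do not bound the true usual-care mean. A reader might infer that the study as a whole is uninformative. It is not: discharge within 36 h of surgery, average stay, adverse events, readmission and acceptance can all be reported from the one series.

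**What to change.** 1. **One clock.** Reconcile sections 2, 3, 4.1 and 5.2.5 on when stay starts, and state whether the 24 h pre-operative admission applies under ERAS. Record admission, end-of-surgery and discharge times for each patient. Assess the 36 h question from surgery, as research question 3 words it. Cost: three recorded times per patient.

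2. **Default: limit the conclusions.** In the title and sections 2, 3, 4.1, 4.2 and 7, remove reduction in stay, turnover gain, cost benefit and cost-effectiveness as conclusions. Report the proportion discharged within 36 h of surgery with an exact 95% confidence interval and stay with a 95% confidence interval; describe bed-hours per case and cost per patient. Do not present 72 h as a measured baseline. Cost: rewording and a more modest claim.

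3. **Alternative, if comparative conclusions are kept.** Extract stay, bed-hours and cost from hospital files for the 12 months before ERAS starts, using the eligibility actually applied to the ERAS series. Report before-after differences with 95% confidence intervals, labelled non-randomised. Claim cost-effectiveness only if differences in both cost and effect are reported. Make no advance statement about the detectable difference, because no SD is given. Cost: up to about 75 files at the stated annual volume, fewer after eligibility is applied. Old cost records may have gaps, and other changes over time cannot be excluded. The file-records activity in section 11 may cover part of the work.

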### **3. Research Questions**

- Is ERAS protocol implementable in Rwanda Tertiary Hospital?
- Is laparoscopic cholecystectomy feasible, safe and cost-effectiveness in the context of ERP in our settings?
- Is possible to discharge laparoscopic cholecystectomy patients within 36 hours postoperative?

## **4. Objectives of the study**

### **4.1. General Objective**

The general objective of this study is to test the implementation of ERAS protocol in laparoscopic cholecystectomy with the aim of decreasing of the length of hospital stay to 36 hours and assess its safety and patients' acceptance.

### **4.2. Specific Objectives**

1. To assess the level of knowledge and practice of Health care professional about Enhanced recovery after surgery program.
2. To determine the frequency of postoperative adverse events and complications after laparoscopic cholecystectomy (tress, fatigue, nausea and vomiting)
3. To determine the average length of hospital stay and bed turn over after laparoscopic cholecystectomy
4. To determine the rate and reason of overnight and re-admissions
5. To assess the patients' acceptance of ERAS program and the overall satisfaction
6. To determine the patient cost benefit when ERAS is implemented correctly.

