#### **5.3. Data collection and analysis**

A baseline survey will be conducted to assess the awareness and knowledge of health care professional in charge of perioperative care. From November 2021, we will put in place an ERAS protocol for laparoscopic cholecystectomies. Patients living in Kigali and near Kigali having an easy communication means will be sensitized to adhere to the program.

A multidisciplinary team (Surgeons, Anesthesiologists, nurses, anesthetists and psychologists) will be mobilized to participate in the team. A google sheet questionnaire will be designed to collect information about the awareness and knowledge of perioperative health care professional about ERAS programme and then

a modified ERAS protocol will be put in place and data collection will be done using a coded checklist form and consecutive selection of patients will be done during the study period until we reach at least 50 patients. The operative procedures and instrumentation will be standardized for laparoscopic cholecystectomy, and surgeons who will perform the procedures will be having expertise in laparoscopic cholecystectomy. Reasons for conversion from laparoscopic to open cholecystectomy will be recorded and documented. Emergency patients and patients defined as ASA IV and pediatric patients aged below 16 years will be excluded.

Data will be collected for age, gender, indications for surgery, American Society of Anesthesiology (ASA) class, operative time, adverse events (pain, nausea and vomiting), length of hospitalization, and intra- and post-operative complications. The expenses of surgery and in-hospital care will be calculated and analyzed. On discharge, on day 3 of discharge, day 10, day 15 and day 30 of discharge patient will report outcomes and will be recorded by Surgical Recovery Scale. After discharge, the patients will be called or texted on phone to know about their status and collect information. Data will be recorded using EXCEL. Statistical analysis will be done using SPSS software and the one-way analysis of variance (ANOVA) test, the Chi-square test, and the t Student's test will be used when appropriate for comparisons.

A Univariate analysis will be done to determine variables associated with the length of hospital stay. Pearson's chi square will be calculated to compare variables and..

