Continuous variables were presented as mean  $\pm$  standard deviation or median (range) when appropriate and categorical variables will be presented as frequency (percentage). A Univariate analysis will be performed through a stepwise linear regression model using length of hospital stay as dependent variable and age, BMI, gender, ASA score, intraoperative infusions, pain, analgesia, nausea, vomiting, 30 days-readmission rates, presence of complications and mortality as independent factors. Variables with significant link will be crossed with outcome variables to draw their correlation overnight, using Multivariate logistic regression A p value  $< 0.05$  will be considered statistically significant.

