## **6. Expected Results**

Table 1: Level of awareness and knowledge of ERAS among perioperative care health professionals

Table 2: Baseline characteristics of patients

Table 2: Acceptance rate of patients in ERP

Table 3: Rate of adverse events (Stress, fatigue, pain, nausea and Vomiting)

Table 4: Complications of laparoscopic cholecystectomy

Table 5: The average length of hospital stay

Tableau 6: Cost of laparoscopic cholecystectomy

Table 7: Rate of overnight and readmission

Table 8: Overall satisfaction of patients after laparoscopic cholecystectomy in ERP

Table 9: Comparative analysis of length and independents variables

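### Objective 1 covers staff knowledge and practice of ERAS, but the survey, its questionnaire and Table 1 cover only awareness and knowledge, so practice has no stated measurement

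*Protocol*

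**What the plan says.** Protocol section 4.2 sets as its first objective: "To assess the level of knowledge and practice of Health care professional about Enhanced recovery after surgery program". It names two things to be assessed, knowledge and practice.

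Section 5.3 says how the staff data will be obtained. It opens with: "A baseline survey will be conducted to assess the awareness and knowledge of health care professional in charge of perioperative care". It then describes the instrument: "A google sheet questionnaire will be designed to collect information about the awareness and knowledge of perioperative health care professional about ERAS programme". The modified pathway follows the survey, and its start is dated: "From November 2021, we will put in place an ERAS protocol for laparoscopic cholecystectomies".

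Section 6 lists one output for this objective: "Table 1: Level of awareness and knowledge of ERAS among perioperative care health professionals".

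**The concern.** The objective and its implementation do not match. The questionnaire determines which data will exist, so a later analysis plan cannot supply practice data that nobody collected.

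The missing half matters to the study's own aims. Section 3 asks whether ERAS can be implemented in a Rwandan tertiary hospital, and section 4.1 makes testing implementation the general objective. Staff may already carry out some pathway elements, such as antibiotic prophylaxis or prevention of nausea and vomiting, without calling them ERAS. A survey of awareness and knowledge would not show this. The report could then say what staff knew about ERAS, but not systematically which elements were already routine and which were new.

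Timing adds some urgency. A clean account of usual practice is easiest to get from staff before they are trained in the pathway and use it daily. Later, their answers about earlier habits may be coloured by what they have since learned.

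**Working it through.** No arithmetic underlies the main point. The check sets the objective beside every place in the protocol that could supply the data.

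**1. Objective against implementation**

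| Place in the protocol | Knowledge or awareness | Practice |
|---|---|---|
| Section 4.2, objective 1 | yes | yes |
| Section 5.3, description of the survey | yes | no |
| Section 5.3, description of the questionnaire | yes | no |
| Section 6, Table 1 | yes | no |

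All three operational statements (3 of 3) omit practice.

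**2. Could another source fill the gap?**

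- *Patient data items, section 5.3.* The list begins "Data will be collected for age, gender, indications for surgery, American Society of Anesthesiology (ASA) class, operative time" and continues with adverse events, length of stay, complications and expenses. It names no item on staff practice or on adherence to pathway elements. These data come from the checklist used once the modified protocol is in place.
- *Regression covariates, section 5.3.* The model includes "intraoperative infusions, pain, analgesia, nausea, vomiting, 30 days-readmission rates, presence of complications and mortality as independent factors". Of these, infusions and analgesia describe care given, but for patients treated under ERAS. They are not a measure of staff practice across the pathway.
- *Other tables, section 6.* The remaining tables cover patient characteristics, acceptance, adverse events, complications, stay, cost, readmission, satisfaction and the analysis of stay. None reports staff practice.
- *Problem statement, section 2.* Current care is described in narrative only: admission 24 hours before surgery, discharge for most patients within two to three days, and complications around 5%. Apart from stay and complications, little is said about the individual pathway elements.
- *Medical files.* Section 11 names these as a data source. No review of files from before the pathway is described, and nothing is said about how complete they are.

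**3. Number of elements a practice question would cover**

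Section 5.2.1 numbers the elements in four columns, with some numbers used twice. Counting entries rather than printed numbers:

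- preoperative (1, 2, 3, 4, 5, 5, 6): 7
- intraoperative (1, 2, 3, 4, 4, 6, 7, 8, 8): 9
- postoperative (1 to 9): 9
- post-discharge (1 to 3): 3

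7 + 9 + 9 + 3 = 28.

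**4. Is there time to correct it?**

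The timetable in section 9 starts data collection in July 2021, and section 5.3 starts the pathway in November 2021. July to October gives four months. The timetable does not say in which month the survey runs, so this window is an inference. The questionnaire is described as still to be designed.

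**The case against.** The best defence is that this is a difference of wording. The questionnaire does not exist yet, item content normally sits in the instrument, and nothing forbids practice items. The staff survey also feeds none of the analyses of stay, safety, cost or readmission. The last point stands and limits the importance of the matter. The first is weaker, because the protocol states the survey's content twice and its output once, and leaves practice out each time.

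A second defence is that objective 1 does not say practice *before* ERAS. It could mean delivery of the pathway once in place, and the coded checklist, which is not reproduced, might record that. The listed items are evidently not exhaustive, since BMI, infusions and analgesia appear only in the regression. It is true that the pre-ERAS reading is inferred from the word baseline in section 5.3. But on either reading no stated item or table reports practice.

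A reader might also infer four stronger things that the documents do not support:

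- *That baseline practice is lost for good once the pathway starts.* The medical files named in section 11 may hold some charted elements. Their completeness is not stated, so neither recovery nor loss can be asserted.
- *That baseline practice would be known for none of the 28 elements.* Minimally invasive access is one of them, and section 5.1 says the hospital already performs laparoscopic surgery routinely, with 75 laparoscopic cholecystectomies a year.
- *That this gap is why a short stay or few adverse events could not be credited to ERAS.* That limitation comes from the absence of a measured comparison group. A self-report survey would not cure it.
- *That knowledge must sit near the floor and is therefore the less useful half.* Section 1 does say "ERAS is not known in Rwanda and there is no report from any sub African country", but this is a background assertion that the survey itself would test.

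**Conclusion.** The mismatch is real. One of the two components named in objective 1 has no stated data source and no output table, and following the protocol as written would leave it unmeasured. Staff reports collected after training would be a poorer substitute, and a chart review might recover part of the information, but neither is planned.

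The point is worth correcting but limited in reach. It concerns one of six specific objectives and leaves the analyses of stay, safety and cost as they are. It rests on two assumptions: that the survey's stated content is what will be built, and that the baseline survey is where practice was meant to be measured. If practice was meant as delivery during ERAS, the gap remains but the remedy would lie in the checklist and its table, and the objective should say so.

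**What to change.** Either of two changes brings the sections into line.

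1. **Measure practice.** Build the questionnaire around the 28 elements in section 5.2.1. For each, ask whether the respondent knows it is part of ERAS and how often it is currently done for laparoscopic cholecystectomy patients (never, sometimes, usually, always). Complete the survey before any ERAS training or the first ERAS patient, whichever comes first. Amend both descriptions in section 5.3, and retitle Table 1 to awareness, knowledge and current practice, reported element by element.
2. **Narrow the objective.** If practice data are not wanted, delete practice from objective 1.

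The first costs a slightly longer online form, with no added visits or staff, and yields self-reported rather than observed practice. The second costs one word, but gives up the description of usual care. The first is preferable while the form is still undesigned. It describes baseline practice only: it does not measure delivery of the pathway and does not allow outcomes to be attributed to ERAS.
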